Visit Window	End-of-treatment Visit	Safety Follow-up Visit/Call (Telephone) ^a		Long-term Follow-up	Survival Follow-up
	Within 7 Days after Last Dose or EOT Decision	30 Days after Last Dose	70 Days after Last Dose ^k	Until Start of New Anticancer Therapy or Transformation to AML ^b	Every 2 Months Until Death or End of Study
	± 7 Days	± 7 Days	± 7 Days	+4 Weeks	
Serum or urine pregnancy test	X			Q4W ^c	Q4W ^c
CBC with differential, platelet count, reticulocytes	X			Q8W ^d	
Serum or plasma chemistry	X				
Peripheral blood for biomarker studies	X				
Pharmacokinetics	X				
Antidrug antibodies	X				
Bone marrow biopsy and aspirate for MRD monitoring and cytogenetics ^{d,e}	X			Q8W ^d	
Response assessment ^{e,f}	X			Q8W ^d	
ECOG	X				
Vital signs	X				
Symptom-directed physical examination	X				
PRO assessment ^g	X			X	
Adverse events ^h	X	X	X		
Concomitant medications	X	X	X		
Blood transfusion ⁱ				X	X
New anticancer therapy ^j				X	X
Survival follow-up					Q2M

Abbreviations: AE = adverse event; AML = acute myeloid leukemia; CBC = complete blood count; CR = complete remission; eCRF = electronic case report form; EOT = end of treatment; EQ-5D-5L = 5-level EuroQol 5 dimensions; FACT-Anemia = Functional Assessment of Cancer Therapy-Anemia; IWG = International Working Group;

MDS = myelodysplastic syndrome; MRD = minimal residual disease; PGIC = Patient Global Impression of Change; PGIS = Patient Global Impression of Severity; PR = partial remission; PRO = patient-reported outcome; QxM = every x months; QxW = every x weeks; SAE = serious adverse event.

- a If the participant experiences a treatment-related AE or an SAE (regardless of attribution), the participant must be asked to come to the site.
- b Until start of new anticancer therapy or transformation to AML, whichever comes first.
- c Collect until the end of the contraception requirement.
- d Bone marrow assessment, MRD, CBC, and response assessment should be performed until start of new anticancer therapy or transformation to AML, whichever comes first. Conventional cytogenetic testing (per institutional standards) is required for all participants.
- e For participants who come off the study treatment to undergo a stem cell transplant, response assessments for relapse/remission status and bone marrow aspirate results are required to be obtained locally and entered into the eCRF.

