6. EFFICACY ANALYSES

6.1. Primary Efficacy Endpoints

6.1.1. Definition of Primary Efficacy Endpoints

The two primary efficacy endpoints of this study are CR rate and OS.

CR Rate: The CR rate is the proportion of patients who reach morphologic CR (morphological blast of \leq 5% and recovery of ANC, platelets, and hemoglobin from complete blood counts as well as peripheral blast) based on Investigator-assessed IWG 2006 MDS criteria {Cheson 2006} on or prior to initiation of any new anticancer therapy, including SCT.

Overall Survival: The OS is measured from the date of randomization to the date of death from any cause. Those who are not observed to die during the study will be censored at their last known alive date.

The date of the last known alive will be determined by selecting the last available visit date across all datasets.

For participants who come off the study, study staff may use public records (eg, public health records) to obtain information about survival status where allowable by local regulation.

Every attempt will be made to ensure that complete death dates are recorded. In those rare instances where complete death dates are not recorded, the following algorithm will be used:

- If day is missing but the month and year are available, then the imputed date will be the 1st day of the month or the last known alive date + 1, whichever is later.
- If day and month are missing but year is available, then the imputed date will be 01Jan of that year or the last known alive date + 1, whichever is later.

When the date of initiation of a new anticancer therapy other than the study treatment or the date of SCT is incomplete or missing, the following algorithm will be followed:

- If the day is missing but the month and year are available, then the imputed day will be the first day of the month or the day of last dose + 1 if the month and year of new anti-cancer therapy and the month and year of last dose are the same.
- If day and month are missing but year is available, then the imputed day and month will be 01Jan or the date of last dose + 1 if the year of new anti-cancer therapy and the year of last dose are the same.

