6.1.3. Analysis of the Primary Efficacy Endpoints

The primary analysis of CR rates was done at the 1st interim efficacy analysis (data cut date: 12Aug2022) based on the first 348 randomized patients in the ITT Analysis Set using the Cochran-Mantel-Haenszel (CMH) test, stratified by the stratification factors at randomization. The odds ratio comparing the 2 arms adjusted for the stratification factors was presented along with 95% confidence interval (CI).

The point estimate of the CR rate and the corresponding 2-sided exact 95% CI based on the Clopper-Pearson method was provided for each arm. Patients, who are randomized but have no on-study response assessment or receive any new anticancer therapy including SCT prior to achieving CR, are considered as non-responders.

If the CR rate of experimental arm is higher than that of control arm and 2-sided p-value from the stratified CMH test using SAS procedure freq is less than 0.03, the null hypothesis of CR rate in Section 6.1.2 would be rejected and the superiority of experimental arm to control arm in terms of CR rate is established.

The primary analysis of OS will compare the OS distributions of two treatment groups using the stratified log-rank test, stratified by the stratification factors at randomization for the ITT Analysis Set. Medians, Q1, Q3 of the OS distributions, and the proportion of patients who are alive at 6, 12, 18 and 24 months from randomization will be estimated along with corresponding 95% CIs using the Kaplan-Meier method. Kaplan-Meier curves will be provided by treatment group.

If the median survival time of experimental arm is longer than that of control arm and two-sided p-value from the stratified log-rank test using SAS procedure Lifetest is less than the cutoff p-values based on observed number of OS events by the data cutoff date as mentioned in Section 2.1, the null hypothesis of OS in Section 6.1.2 will be rejected and the superiority of experimental arm to control arm in terms of OS is established.

In addition, the HR between the 2 treatment groups and its 95% CI will be estimated using the Cox proportional hazards regression model stratified by the stratification factors. For pre-specified non-binding futility analysis boundary of HR=0.95 at the second interim analysis if CR was not statistically significant, the HR from the Cox model will be used to check whether the futility boundary has been crossed or not.

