Event-free Survival: The EFS is defined as the time from randomization to transformation to AML or death from any cause, whichever occurs first. Transformation assessments and deaths post SCT will be included in the analysis. Patients who are not observed to have one of these events during the study will be censored at their last response assessment date with evidence of no transformation to AML. If patients start taking new anticancer therapies (excluding SCT) before transformation to AML or death, EFS will be censored at the last response assessment on or before the initiation of the new anticancer therapies. Patients will be censored at the date of randomization if no response assessment performed after randomization and the patients didn't die.

CR in TP53 Mutant Population: CR in TP53 Mutant Population is defined as the proportion of patients who achieve a morphologic CR based on Investigator assessments using IWG criteria {Cheson 2006} on or prior to initiation of any new anticancer therapy, including SCT in TP53 mutant population.

MRD-negative Response Rate: The MRD-negative response rate is defined as the proportion of patients who achieve a morphologic CR or marrow CR based on Investigator assessments using IWG criteria {Cheson 2006} and reach MRD-negative disease status on or prior to initiation of any new anticancer therapy, including SCT. MRD-negative disease status will be assessed using a multiparameter flow cytometry-based assay performed by a central laboratory.

Time to Transformation to AML: Time to transformation to AML is defined as the time from randomization to transformation to AML. Patients who are not observed to have transformation to AML will be censored at their last response assessment date with evidence of no AML diagnosis. Transformation assessments post SCT will be included in the analysis. If patients start taking new anticancer therapies (excluding SCT) before documented AML diagnosis, Time to Transformation to AML will be censored at the last response assessment on or before the initiation of the new anticancer therapies. Patients will be censored at the date of randomization if no response assessment performed after randomization.

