Progression-free Survival: PFS is defined as the time from randomization to the date of documented disease progression (including treatment failure by IWG criteria or relapse after PR/CR), or death from any cause, whichever occurs first. Response assessments and deaths post SCT will be included in the analysis. Those who are not observed to have one of these events will be censored at their last response assessment date with evidence of no disease progression/relapse. If patients start taking new anticancer therapies (excluding SCT) before disease progression (including treatment failure by IWG criteria or relapse after PR/CR) or death, PFS will be censored at the last response assessment on or before the initiation of the new anticancer therapies. Patients will be censored at the date of randomization if no response assessment performed after randomization and the patients didn't die.

FACT-Anemia Response Rate: The FACT-Anemia response rate is defined as the proportion of patients who showed clinically meaningful improvement in health-related quality of life (HRQoL) based on the score from the FACT-Anemia instrument on or prior to initiation of any new anticancer therapy, including SCT {Cella 2002}. The minimal clinically meaningful difference of 7.0 as suggested in the referenced literature will be used as cutoff for clinically meaningful improvement. Patients, who are randomized but have no baseline or no postbaseline FACT-Anemia questionnaire assessment or receive any new anticancer therapy including SCT prior to achieving the FACT-Anemia response, will be considered as non-responders.

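### A partial start date for new non-transplant therapy can be imputed before the post-dose marrow that first shows progression, AML or a response

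*SAP*

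**What the plan says.** SAP 6.1.1 gives the rule for an incomplete start date of new anticancer therapy or SCT. With the day missing, "then the imputed day will be the first day of the month or the day of last dose + 1", the latter when therapy and last dose share month and year. With day and month missing, the date becomes "01Jan or the date of last dose + 1 if the year of new anti-cancer therapy" matches the year of last dose. Last dose is the only participant-specific bound. The death-date rule in the same section does use later knowledge of the participant: "the imputed date will be the 1st day of the month or the last known alive date + 1, whichever is later".

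The therapy date then drives several analyses:

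- **Time-to-event endpoints (SAP 6.2.1, Table 6-2).** "EFS will be censored at the last response assessment on or before the initiation of the new anticancer therapies", and likewise "PFS will be censored at the last response assessment on or before the initiation of the new anticancer therapies". Time to AML follows the same pattern. SCT does not censor these endpoints.
- **Response endpoints (SAP 6.1.1, 6.1.3, 6.2.1).** Responses must come no later than new therapy or SCT. For CR, participants who "receive any new anticancer therapy including SCT prior to achieving CR, are considered as non-responders".
- **Safety (SAP 7.1.5.1, 7.2).** The TEAE and laboratory windows close the day before new therapy if that comes before their fixed limits of 70 and 30 days after last dose.

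In Protocol Table 5 the end-of-treatment visit falls "Within 7 Days after Last Dose or EOT Decision", with a ±7-day window. Follow-up assessments come every 8 weeks, and footnote d says that "response assessment should be performed until start of new anticancer therapy or transformation to AML".

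**The concern.** Scheduled assessments outside SCT stop when new therapy starts. A scheduled marrow dated in the same known month or year as the therapy should therefore precede it. The imputation ignores this and takes the earliest possible day. A marrow taken after the last dose can then fall after the imputed start, although the true order was the reverse.

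For PFS, EFS and time to AML, an observed event is replaced by censoring at an earlier assessment. That censoring is informative, because it happens to participants whose disease has just been shown to worsen. For ORR, MRD-negative response and CR in the TP53-mutant population, a response first shown on that marrow becomes a non-response. Early imputation is therefore conservative for response rates but not for the time-to-event endpoints. The post-dose TEAE window can also shrink, to nothing in some cases.

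**Working it through.** The plan states no figure for this point, so there is none to reproduce. The check applies the rule literally, first to worked dates and then to simulated ones.

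**Rule as coded.** Month known: imputed start = last dose + 1 if therapy and last dose share month and year, otherwise the first of the month. Year only: last dose + 1 if they share the year, otherwise 01 Jan. A marrow is lost if its date is later than the imputed start. Post-dose TEAE days = min(last dose + 70, start - 1) - last dose.

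**Worked dates (2022, illustrative)**

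| Case | Last dose | Marrow | True start | Known | Imputed | Marrow | TEAE days, true / imputed |
|---|---|---|---|---|---|---|---|
| A | 05 Sep | 12 Sep | 26 Sep | month | 06 Sep | lost | 20 / 0 |
| B | 29 Aug | 08 Sep | 22 Sep | month | 01 Sep | lost | 23 / 2 |
| C | 10 Feb | 15 Aug | 05 Sep | month | 01 Sep | kept | 70 / 70 |
| C | 10 Feb | 15 Aug | 05 Sep | year | 11 Feb | lost | 70 / 0 |

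The window falls to zero in A and in year-only C, where therapy and last dose share the known month or year. In B they do not, and 2 days remain.

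**Simulation.** There were 100,000 participants per scenario, all with a partial date and a post-dose marrow. Last doses were uniform over two years, and marrow and therapy delays uniform over the ranges shown. The 0-14 day range is the 7-day visit limit plus the 7-day window. The therapy delays are assumptions; the documents give none.

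| Marrow after last dose | Therapy after marrow | Lost, month known | Lost, year only | Mean TEAE days: true / month / year |
|---|---|---|---|---|
| 0-14 d | 1-14 d | 62% | 85% | 13.5 / 3.8 / 0.3 |
| 0-14 d | 1-28 d | 42% | 83% | 20.6 / 8.6 / 0.7 |
| 0-14 d | 14-56 d | 8% | 78% | 41.0 / 26.6 / 2.6 |
| 14-180 d | 1-14 d | 72% | 98% | 62.5 / 57.3 / 13.6 |
| 14-180 d | 1-28 d | 49% | 96% | 64.3 / 59.6 / 14.7 |
| 14-180 d | 14-56 d | 10% | 90% | 68.0 / 65.2 / 18.6 |

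**Hand check.** For a year-only date in the same year as last dose, only marrows on day 0 or 1 survive. With 15 equally likely days (0-14), the loss is 13/15 = 87%. The simulated 78-85% is a little lower because some therapies start in the next calendar year.

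**Scale.** For every 10 participants whose decisive result is on a post-dose marrow and whose therapy date is partial, these scenarios lose about 1 to 7 results with the month known (10 × 0.08 to 10 × 0.72) and about 8 to 10 with only the year (10 × 0.78 to 10 × 0.98).

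**The case against.** The strongest objection is that the marrow prompting a change of therapy is often already protected. Table 5, footnote f, waives the end-of-treatment response assessment if one was done in the last 30 days or progression is documented. Protocol 5.7.1 advises treating on until progression is confirmed at least 4 weeks later. On that path the decisive marrow falls on or before the last dose, where the existing floor keeps it. A reader might infer that the rule generally discards the events that caused the switch. The documents do not support that. The simulation places every marrow on or after the last dose, so its percentages describe only the exposed subset.

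Other points also stand. A marrow first showing CR will seldom lead to non-transplant therapy. Partial dates should be uncommon, since survival contacts are every 2 months and queries are resolved before analysis. Key secondary endpoints are formally tested only after OS is rejected, and then in sequence. AEs outside the window stay in the all-AE listing (SAP 7.1.6.1).

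An added floor also carries a risk. Protocol 4.1 follows participants who stop for reasons other than progression until progression, without naming new therapy as an end. SAP 3.8.2 admits unscheduled response assessments. A marrow taken after new therapy could then be treated as before it and credit a response. The current rule is the more conservative one for response.

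These points limit the reach and shape the fix. None removes the mechanism, and no other text in either document corrects the imputed date.

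**Conclusion.** The point holds in a limited form. It applies to participants with a partial start date for non-transplant therapy whose progression, AML or response is first shown on a marrow after the last dose. For them the rule can replace an observed PFS, EFS or time-to-AML event with informative censoring, or a response with a non-response. The post-dose TEAE window falls to zero only when therapy and last dose share the known month or year.

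Three stronger readings are not supported:

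- **That a primary test is at risk.** OS does not use this date. The primary CR test was completed at the first interim analysis (cut 12 Aug 2022), and this SAP governs the second interim and final analyses.
- **That the trial-wide loss can be counted, or that one arm is favoured.** The documents give neither the number of switchers nor the share with partial dates, by arm or overall. The number is probably small.
- **That the same floor should apply to SCT dates.** Assessments continue after SCT, so they do not bound its date.

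The loss percentages rest on assumed timings and are sensitive to them. With the month known they run from 8% to 72% over the scenarios tabulated. This is a cheap improvement, not a threat to the main conclusions.

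**What to change.** In SAP 6.1.1, for non-SCT therapy, impute the start as the latest of:

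- (a) the first day of the known month, or 01 Jan of the known year;
- (b) last dose + 1;
- (c) the date of the last scheduled response assessment within that known month or year.

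Cap the result at the end of that month or year and at death. Use the same date for the TEAE and laboratory cutoffs. Leave the partial SCT date rule unchanged.

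Because the SAP counts assessments on the start date itself, (c) needs no extra day. In case A the start becomes max(01 Sep, 06 Sep, 12 Sep) = 12 Sep: the marrow is kept and the post-dose TEAE window is 6 days instead of 0. In B it becomes 08 Sep (9 days instead of 2). In year-only C it becomes 15 Aug (70 days instead of 0).

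The cost is a sentence or two of SAP text and a small programming change, best made before data finalization for the second interim analysis. The downside is that a marrow done after new therapy, against the schedule, would count as before it and could credit a response. List such cases, and report the response endpoints under the current rule as a sensitivity analysis.

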6.1.2. Statistical Hypothesis for the Primary Efficacy Endpoints

The first primary efficacy hypothesis was tested on CR rate difference between magrolimab + azacitidine (experimental arm) and placebo + azacitidine (control arm) based on the first 348 randomized patients at the 1st planned interim efficacy analysis. Using CR rate_{exp} and CR rate_{ctrl} to denote the CR rates for the experimental arm and control arm, respectively, the statistical hypotheses tested in this study is:

 H_0 : CR rate_{exp} = CR rate_{ctrl}

 H_1 : CR rate_{exp} \neq CR rate_{ctrl} (experimental arm is not equal to control arm in terms of CR rate)

The second primary efficacy hypothesis to be tested is that there is no difference between magrolimab + azacitidine (experimental arm) and placebo + azacitidine (control arm) in OS for patients. Using $S_{exp}(t)$ and $S_{ctrl}(t)$ to denote the OS distribution functions of the experimental arm and control arm, respectively, the statistical hypotheses to be tested in this study will be:

 $H_0: S_{exp}(t) = S_{ctrl}(t)$ at all time points t

 $H_1: S_{exp}(t) \neq S_{ctrl}(t)$ (experimental arm is not equal to control arm in terms of OS for some t > 0)

6.1.3. Analysis of the Primary Efficacy Endpoints

The primary analysis of CR rates was done at the 1st interim efficacy analysis (data cut date: 12Aug2022) based on the first 348 randomized patients in the ITT Analysis Set using the Cochran-Mantel-Haenszel (CMH) test, stratified by the stratification factors at randomization. The odds ratio comparing the 2 arms adjusted for the stratification factors was presented along with 95% confidence interval (CI).

The point estimate of the CR rate and the corresponding 2-sided exact 95% CI based on the Clopper-Pearson method was provided for each arm. Patients, who are randomized but have no on-study response assessment or receive any new anticancer therapy including SCT prior to achieving CR, are considered as non-responders.

If the CR rate of experimental arm is higher than that of control arm and 2-sided p-value from the stratified CMH test using SAS procedure freq is less than 0.03, the null hypothesis of CR rate in Section 6.1.2 would be rejected and the superiority of experimental arm to control arm in terms of CR rate is established.

The primary analysis of OS will compare the OS distributions of two treatment groups using the stratified log-rank test, stratified by the stratification factors at randomization for the ITT Analysis Set. Medians, Q1, Q3 of the OS distributions, and the proportion of patients who are alive at 6, 12, 18 and 24 months from randomization will be estimated along with corresponding 95% CIs using the Kaplan-Meier method. Kaplan-Meier curves will be provided by treatment group.

If the median survival time of experimental arm is longer than that of control arm and two-sided p-value from the stratified log-rank test using SAS procedure Lifetest is less than the cutoff p-values based on observed number of OS events by the data cutoff date as mentioned in Section 2.1, the null hypothesis of OS in Section 6.1.2 will be rejected and the superiority of experimental arm to control arm in terms of OS is established.

In addition, the HR between the 2 treatment groups and its 95% CI will be estimated using the Cox proportional hazards regression model stratified by the stratification factors. For pre-specified non-binding futility analysis boundary of HR=0.95 at the second interim analysis if CR was not statistically significant, the HR from the Cox model will be used to check whether the futility boundary has been crossed or not.

